8.4.1 Hematologic Toxicity

Worst Hematologic Toxicity*	Management
Grade 1 or 2	Maintain dose level
Grade 3 or 4 neutropenia Grade 3 thrombocytopenia	Omit dose until resolved to \leq grade 1 (or baseline) then: If resolved in \leq 7 days, then maintain dose level If resolved in $>$ 7 days, then decrease one dose level ***
Grade 4 thrombocytopenia	Omit dose until resolved to \leq grade 1 (or baseline) then decrease one dose level ***
Febrile neutropenia**	Omit dose until resolved to \leq grade 1 then decrease one dose level

* As defined according to IW CLL guidance in Section 8.3.
 ** ANC $< 1 \times 10^9/L$ with a single temperature of $\geq 38.3^\circ\text{C}$ or a sustained temperature of $\geq 38^\circ\text{C}$ for more than one hour.
 *** After treatment is resumed at a lower dose, if the same toxicity recurs with the same severity, then the next treatment should be resumed at a lower dose regardless of duration. If the same toxicity occurs with a worse severity, then the patient must discontinue treatment with buparlisib.
 If a third dose reduction is required, patients must discontinue protocol therapy.
 If therapy is delayed by $>$ 28 days, patients must discontinue protocol therapy.

8.4.2 Renal Toxicity

Worst Toxicity Serum creatinine	Management
Grade 1	Maintain dose level
Grade 2 ($> 1.5-3 \times$ baseline or ULN)	Omit dose until resolved to \leq grade 1 (or baseline) then: If resolved in \leq 7 days, then maintain dose level If resolved in $>$ 7 days, then decrease one dose level*
Grade 3 or 4 ($> 3 \times$ baseline or ULN)	Permanently discontinue buparlisib

* After treatment is resumed at a lower dose, if the same toxicity recurs with the same severity, then the next treatment should be resumed at a lower dose regardless of duration. If the same toxicity occurs with a worse severity, then the patient must discontinue treatment with buparlisib.
 If a third dose reduction is required, patients must discontinue protocol therapy.
 If therapy is delayed by $>$ 28 days, patients must discontinue protocol therapy.

8.4.3 Hepatic Toxicity

In event of hepatotoxicity, consider alternate causes (cholestasis, viral, malignant, concomitant medication, etc.) and refer to hepatologist as clinically indicated.

Bilirubin*	Dose of buparlisib****	Follow-up
Grade 1	No change	See Section 9
Grade 2 (> 1.5 - 3.0 x ULN) with ALT or AST \leq 3.0 x ULN	Omit dose until resolved to \leq grade 1 then: If resolved in \leq 7 days, maintain dose level If resolved in > 7 days, decrease one dose level**	LFTs weekly or more frequently if clinically indicated until resolved to \leq grade 1.
Grade 3 (> 3.0 - 10.0 x ULN) with ALT or AST \leq 3.0 x ULN	Omit dose until resolved to \leq grade 1 then: If resolved in \leq 7 days, decrease one dose level** If resolved in > 7 days, discontinue buparlisib	LFTs weekly or more frequently if clinically indicated until resolved to \leq grade 1, then every other week until off treatment and recovered to \leq grade 1
Grade 4 (>10 x ULN)	Discontinue buparlisib	LFTs weekly or more frequently if clinically indicated until resolved to \leq grade 1 (or stable)
AST or ALT		
Same grade as baseline:	No change	See Section 9
Increase from baseline: • < 1.5 ULN at baseline, increases to 1.5 to < 3 x ULN • Grade 1 to grade 2	Continue with a one dose level reduction	LFTs weekly or more frequently if clinically indicated until resolved to \leq grade 1
Increase of two grades from baseline: • Grade 0 to Grade 2*** • Grade 1 to Grade 3***	Omit dose until resolved to \leq grade 1 then reduce 1 dose level**. If no recovery \leq 28 days, permanently discontinue buparlisib.	LFTs weekly or more frequently if clinically indicated until resolved to \leq grade 1, then every other week until off treatment and recovered to \leq grade 1
Grade 4 (> 20.0 x ULN)	Discontinue buparlisib	LFTs weekly or more frequently if clinically indicated until resolved to \leq grade 1 (or stable)
AST/ALT and bilirubin*		
AST or ALT > 3 x ULN (grade 2) and total bilirubin > 2 x ULN	Discontinue buparlisib	LFTs weekly or more frequently if clinically indicated until resolved to \leq grade 1 (or stable)

* If known Gilbert's, use direct bilirubin to grade
 
** After treatment is resumed at a lower dose, if the same toxicity recurs with the same severity, then the next treatment should be resumed at a lower dose regardless of duration. If the same toxicity occurs with a worse severity, then the patient must discontinue treatment with buparlisib.
 
*** If grade 2 or 3 and bilirubin > 2 x ULN, meets criteria below to discontinue buparlisib. In case of recurring Grade 3 or higher toxicity after re-challenge, buparlisib should be permanently discontinued.
 
**** If a third dose reduction is required or therapy is delayed by > 28 days, patients must discontinue protocol therapy.
		

AMEND #1: 2015-OCT-22; AMEND #3: 2016-AUG-24

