8.4 Dose Adjustments

Dose Level	Daily dosing of buparlisib in 28 day cycle
-1	Reduce by 20 mg daily
-2	Reduce by 20 mg daily
-3	If required patients must discontinue protocol therapy

Doses will be reduced for hematologic and other adverse events considered related to buparlisib. Dose adjustments are to be made according to the system showing the greatest degree of toxicity.

The most frequently observed toxicities with buparlisib include transaminitis, skin toxicity, hyperglycemia, GI effects (diarrhea, anorexia, constipation, nausea, vomiting, mucositis), fatigue, abdominal pain and mood alterations.

The guidelines which follow outline buparlisib dose adjustments for several of these toxic effects. If a patient experiences several toxicities and there are conflicting recommendations, please use the recommended dose adjustment that reduces the dose to the lowest level.

Doses of buparlisib reduced for toxicity may not be re-escalated. For each patient, a maximum of 2 dose reductions will be allowed. Patients requiring an additional dose reduction will stop buparlisib and come off study.

Patients requiring a buparlisib dose delay of > 28 days must permanently discontinue buparlisib and come off study.

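### The hepatic dosing table (Protocol 8.4.3) loses its required hold when bilirubin is > 1.5 to 2.0 x ULN and both transaminases rise from grade 1 to above 3 x ULN

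*Protocol*

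**What the plan says.** Protocol 8.4.3 sets buparlisib dosing by bilirubin, by AST or ALT, and by the two together.

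- **Bilirubin, grade 2.** "Grade 2 (> 1.5 - 3.0 x ULN) with ALT or AST" at or below 3.0 x ULN. The dose is held until grade 1 or lower. It resumes unchanged if recovery takes 7 days or less, and one level lower if it takes longer.
- **AST or ALT, smaller rise.** For grade 1 to grade 2, or from below 1.5 x ULN to between 1.5 and 3 x ULN: "Continue with a one dose level reduction".
- **AST or ALT, larger rise.** The row headed "Increase of two grades from baseline" lists grade 0 to 2 and grade 1 to 3. The dose is held, then reduced one level.
- **AST or ALT, grade 4** (> 20 x ULN). Discontinue.
- **Combined.** AST or ALT > 3 x ULN together with "total bilirubin > 2 x ULN". Discontinue.

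Footnote *** adds: "If grade 2 or 3 and bilirubin > 2 x ULN, meets criteria below to discontinue buparlisib". Footnote **** adds: "If a third dose reduction is required or therapy is delayed by > 28 days, patients must discontinue protocol therapy". Section 8.4 sets the general limits: "For each patient, a maximum of 2 dose reductions will be allowed" and "Doses of buparlisib reduced for toxicity may not be re-escalated". It also says that, when recommendations conflict, the one giving the lowest dose is used.

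**The concern.** The bilirubin hold lapses once both enzymes exceed 3 x ULN, but the combined stop starts only when bilirubin exceeds 2 x ULN. Between these limits no row was written for the two abnormalities together. A patient there falls back on the enzyme rows alone, and for a grade 1 to 2 rise those rows keep the patient on drug at a lower dose.

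As the liver picture worsens, the stated action therefore runs hold, continue at a reduced dose, discontinue. The protocol gives no reason for the middle step. Section 8.4 names transaminitis first among the most frequent toxicities of buparlisib. Grade 1 enzymes at entry are also allowed: 5.1.7 accepts up to 1.5 x ULN, or 3 x ULN with hepatic CLL. What is at stake is drug taken while both markers are abnormal. No effect on the response endpoint is claimed.

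**Working it through.** **Inputs.** The row conditions and actions are those of 8.4.3. The starting dose of 100 mg is from 8.1.1 and the 20 mg reduction step is from 8.4. The protocol prints AST/ALT grade 2 as > 3 x ULN and grade 4 as > 20 x ULN. Two boundaries are assumed: grade 0 is at or below ULN, and grade 1 is above ULN up to 3 x ULN. The cut between grades 2 and 3 is not printed. Values of 4.5, 5 and 8 x ULN were tried and gave the same matches.

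**Step 1: three patients, each with baseline AST and ALT of 1.2 x ULN (grade 1).**

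| Patient | Bilirubin (x ULN) | AST and ALT (x ULN) | Bilirubin grade 2 row | Combined row | Enzyme row | Action |
|---|---|---|---|---|---|---|
| A | 1.8 | 1.2 | applies | no | same grade | hold |
| B | 1.8 | 3.2 | no (both > 3.0) | no (bilirubin not > 2) | grade 1 to 2 | continue at 80 mg |
| C | 2.1 | 3.2 | no | applies | grade 1 to 2 | discontinue |

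With bilirubin 1.8 and only one enzyme above 3 x ULN, the bilirubin row still applies and the action is a hold. The hold goes when the second enzyme crosses 3. Bilirubin of exactly 2.0 behaves as in B. Footnote *** does not help B, because it needs bilirubin > 2 x ULN. The conflict rule in 8.4 does not help either, since only one recommendation applies.

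**Step 2: larger rises at bilirubin 1.8.** Grade 0 to 2, or grade 1 to 3, in both enzymes: hold, then reduce. Grade 0 to 3 in both: no row of 8.4.3 matches. One enzyme grade 1 to 2 and the other grade 0 to 3: only the reduction row matches.

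**Step 3: the whole grid above 1.5 x ULN.** Each enzyme takes one of 7 states: same grade and <= 3 x ULN; from < 1.5 to 1.5-< 3 x ULN; grade 1 to 2; 0 to 2; 1 to 3; 0 to 3; grade 4. Unordered AST/ALT pairs: 7 x 8 / 2 = 28. Bilirubin bands: > 1.5-2.0, > 2.0-3.0, > 3.0-10 and > 10 x ULN. Cells: 28 x 4 = 112. The strictest matching action is taken, with fewer than two earlier reductions.

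| Reading | Cells with neither hold nor stop |
|---|---|
| As printed | 3: (1 to 2, 1 to 2), (1 to 2, 0 to 3), (0 to 3, 0 to 3) |
| As printed, 8.4.8 grade 3 row used for 0 to 3 | 1: (1 to 2, 1 to 2) |
| Bilirubin qualifier read as both enzymes <= 3.0 | 7 |
| With the added row, any of these readings | 0 |

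The 7 are the 3 above plus 4 more: either of the two states at or below 3 x ULN paired with grade 1 to 2 or grade 0 to 3 (2 x 2 = 4). All the uncovered cells lie at bilirubin > 1.5-2.0 x ULN.

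**Step 4: drug taken, B against A.** Over d days B takes 80 x d mg. If A's hold lasts 7 days, A resumes at 100 mg and takes 100 x (d - 7) mg.

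| Day | B (mg) | A (mg) |
|---|---|---|
| 7 | 560 | 0 |
| 28 | 2240 | 2100 |
| 35 | 2800 | 2800 |
| 56 | 4480 | 4900 |

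If A's hold lasts H > 7 days, A resumes at 80 mg and takes 80 x (d - H) mg. B then stays ahead by 80 x H: 1120 mg for H = 14 and 2240 mg for H = 28.

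**The case against.** The best defence is that the two rows differ in kind. The bilirubin hold is temporary and may end in a return to full dose. The enzyme row imposes at once a reduction that is never reversed, so after a 7-day hold A has received more drug than B from day 35 onward. B is also watched: liver tests are at least weekly, other causes are to be considered, and hepatology referral is available. Under 8.0 the investigator is responsible for treatment and may interrupt the drug. A patient with two earlier reductions must stop. All of this stands and limits the harm. It does not supply a stated interruption while both markers are abnormal, which the table does require in milder cases.

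The second objection concerns the grade 0 to 3 rise. A three-grade rise could be taken to include a two-grade rise, and the grade 3 row of 8.4.8 would give a hold. That is a sensible way to act, but 8.4.3 does not say so, and 8.4.8 is for other events. This part is the weaker one. Without it, the grade 1 to 2 cell remains, and the grade 2 row of 8.4.8 would also continue dosing there.

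Third, a grade 0 to 3 rise is also unlisted when bilirubin is normal, and a row tied to bilirubin above 1.5 x ULN does not change that. This is correct. The present point covers only bilirubin above 1.5 x ULN.

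**Conclusion.** The concern holds as a minor patient-safety fault in the written rule. With bilirubin > 1.5 to 2.0 x ULN and both enzymes up from grade 1 to 2, the only instruction is to continue one level lower, between a required hold and a required stop. This core cell does not depend on borrowing 8.4.8 or on how the bilirubin qualifier is read. It rests on the assumed upper limit of grade 1 at the printed 3 x ULN cut and on fewer than two earlier reductions. The literal gap for a grade 0 to 3 rise is additional and depends on treating the listed rises as exhaustive.

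The bilirubin window is 0.5 x ULN wide. Cell counts are not probabilities, and the documents give no basis for estimating how many of the up to 29 patients would enter it.

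**What to change.** Add one row to the combined part of the 8.4.3 table. For total bilirubin > 1.5 to 2.0 x ULN with AST or ALT > 3 x ULN, omit buparlisib until both are at or below grade 1, then reduce one dose level. AST or ALT grade 4 still discontinues. This fits the neighbouring rows and closes the gap whichever way the bilirubin qualifier is read, so that wording can stay.

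The change can be made by amendment or clarification memo. It needs no new tests, because bilirubin, AST and ALT are already drawn together. The cost is an occasional extra hold, which counts toward the 28-day delay limit. A patient with two earlier reductions discontinues after a grade 1 to 2 rise under the current text and under the new row alike.

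### Protocol 8.4.3 gives opposite instructions for a recurrent grade 3 bilirubin rise that takes more than 7 and up to 28 days to resolve

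*Protocol*

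**What the plan says.** Four pieces of text in Protocol 8.4.3 bear on a recurrent grade 3 bilirubin rise with ALT or AST at most 3 x ULN.

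- **The grade 3 bilirubin row.** Treatment is held until bilirubin is back to grade 1 or lower. Resolution within 7 days leads to a one-level reduction, and this branch carries the double-asterisk marker. The other branch reads "If resolved in > 7 days, discontinue buparlisib" and carries no marker. Nothing limits the row to a first event.
- **The double-asterisk footnote.** Its condition is "After treatment is resumed at a lower dose". It then says "if the same toxicity recurs with the same severity, then the next treatment should be resumed at a lower dose regardless of duration". A recurrence at worse severity leads to discontinuation.
- **The triple-asterisk footnote.** Its marker is on the AST/ALT row for a two-grade increase. Its last sentence is worded without reference to AST or ALT: "In case of recurring Grade 3 or higher toxicity after re-challenge, buparlisib should be permanently discontinued".
- **The four-asterisk footnote**, on the heading of the dose column: "If a third dose reduction is required or therapy is delayed by > 28 days, patients must discontinue protocol therapy".

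Protocol 8.4 adds two general rules. One is the cap: "For each patient, a maximum of 2 dose reductions will be allowed". The other is a tie-break: "If a patient experiences several toxicities and there are conflicting recommendations, please use the recommended dose adjustment that reduces the dose to the lowest level".

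The SAP does not address dose modification.

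**The concern.** A patient can satisfy the conditions of the row and of the double-asterisk footnote at the same time, and the two then point in opposite directions: permanent stop or restart. Two sites, each following the protocol as written, could manage the same patient differently after a second grade 3 liver signal. What is at stake is patient safety and uniform conduct. A deviation could not be judged either, because each action has text behind it.

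**Working it through.** No sample size, power or error rate is involved, and the protocol states no figure to reproduce. The check is to follow one patient through the text.

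**The case.** A first grade 3 bilirubin event resolves within 7 days. Treatment restarts one level lower, and grade 3 bilirubin then recurs. ALT and AST stay at or below 3 x ULN throughout; otherwise the separate row for combined AST/ALT and bilirubin elevation could apply. Time to resolution is taken as the length of the treatment delay.

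**Can the case arise?** The first event uses reduction 1 and the recurrence would use reduction 2. Since 1 + 1 = 2, the cap in 8.4 is met but not exceeded, and the four-asterisk footnote's third-reduction limit is not triggered. If the patient had already been reduced for another reason, the recurrence would need a third reduction and treatment would stop under that footnote. The conflict therefore needs a second reduction to be still available.

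**Instructions by time to resolution of the recurrence:**

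| Recurrence resolves in | Grade 3 bilirubin row | Double-asterisk footnote | Four-asterisk footnote | Triple-asterisk last sentence, if read generally |
|---|---|---|---|---|
| 7 days or less | reduce one level | restart lower | not triggered | stop |
| more than 7, up to 28 days | stop | restart lower | not triggered | stop |
| more than 28 days | stop | restart lower, overridden by the 28-day limit | stop | stop |

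In the first line the row and the double-asterisk footnote agree. In the second they contradict each other. In the third the outer limit settles the matter. If the triple-asterisk sentence reaches bilirubin, it contradicts the double-asterisk footnote in the first line as well.

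**Does other text resolve it?** The tie-break in 8.4 is worded for several toxicities with competing recommendations. Here there is one toxicity under two rules.

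**Comparison with neighbouring tables.** The same recurrence footnote is attached to other rows with a 7-day test: neutropenia and grade 3 thrombocytopenia in 8.4.1, grade 2 creatinine in 8.4.2, and grade 2 bilirubin in 8.4.3. In each of these the 7-day test separates maintaining the dose from reducing it. Ignoring duration at recurrence removes the option to maintain, so the footnote makes the rule stricter. In the grade 3 bilirubin row the test separates reducing from stopping. The same words then relax a stop, and a slow recurrence is handled less strictly than a slow first event. The protocol does not say that this is intended.

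Two other tables show that the protocol can be explicit. Sections 8.4.4 and 8.4.7 label first and later events separately. The grade 3 hyperglycemia row in 8.4.5 also stops treatment after more than 7 days, but its footnote has no sentence on recurrence.

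**The case against.** **Marker placement.** The double-asterisk marker is on the branch for resolution within 7 days, and the stop instruction is unmarked. A site reading the markers literally finds an unqualified stop. This is a fair point, and a reader should not infer that the footnote is attached to the stop line. It does not remove the conflict. The marked branch is this row's route to a restart at a lower dose, the footnote's condition is exactly that restart, and its recurrence rule applies whatever the duration.

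**Shared wording.** The footnote is used across several tables, where it tightens the rule. The likeliest explanation here is imprecise copying, not two deliberate and opposite rules. That may explain the origin, but the text as printed still gives both instructions.

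**A specific rule overrides a general one.** One could treat the footnote as a recurrence rule that displaces the row, or treat the row's stop as controlling. Both readings are arguable and the protocol chooses neither.

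**The triple-asterisk sentence settles it.** A reader might infer that its permanent stop governs bilirubin too. Its marker is only on the AST/ALT row, so the documents do not establish this. If it did apply, it would conflict with the double-asterisk footnote over a wider range of recurrences.

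**Size and consequence.** A reader might want a percentage for how often resolution falls between day 7 and day 28. The documents give no resolution times, and any such figure would be set by the distribution assumed. A reader might also infer a threat to the primary decision, which turns on 2 responders among 12 evaluable patients (Protocol 14.2). Best response is classified up to the end of treatment (10.4), so an early stop could in principle matter to one patient. But 9.3 requires a confirmatory assessment at 8 weeks for patients who leave treatment with a suspected response, and follow-up every three months for those with ongoing response or stable disease. No effect on the endpoint is shown.

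**Conclusion.** The point holds as a minor internal inconsistency. It is confined to a same-grade recurrence of grade 3 bilirubin, with ALT or AST at most 3 x ULN, after a restart at a lower dose, with a second reduction available and resolution in more than 7 and up to 28 days. In that window the row and the double-asterisk footnote give opposite instructions and nothing else in 8.4 decides between them. If the last sentence of the triple-asterisk footnote is taken to cover bilirubin, the clash with the double-asterisk footnote extends to recurrences resolving within 7 days.

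The chain of events is long and probably uncommon in a trial of up to 29 patients. The list of most frequent toxicities in 8.4 names transaminitis and does not name raised bilirubin. No frequency can be derived from the documents. The conclusion rests on reading the row as covering recurrences, which its wording permits, and on no view about which instruction is clinically right.

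**What to change.** Reconcile the grade 3 bilirubin row in 8.4.3 with the double- and triple-asterisk footnotes so that a single instruction applies to recurrent grade 3 bilirubin. The revised text should state two things:

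1. whether the footnote's disregard of duration overrides the row's 7-day rule;
2. whether the last sentence of the triple-asterisk footnote applies to bilirubin or only to AST/ALT.

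Reconciling only the row and the double-asterisk footnote would leave the second question open. The sponsor decides which instruction applies. The cost is a short clarification in the next amendment or a memo to sites, with no added patients, visits or procedures.

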5.1.7 Laboratory Requirements

(must be done within 7 days prior to registration)

Hematology	Absolute neutrophil counts (ANC)	$\geq 1.0 \times 10^9/L$
	Platelets	$\geq 50 \times 10^9/L$ and more than 5 days since last transfusion
Chemistry	Creatinine clearance*	$\geq 50 \text{ mL/min}$
	Bilirubin**	$\leq 1.5 \times \text{upper normal limit (UNL)}$
	Alanine aminotransferase (AST) and aspartate aminotransferase (ALT)	$\leq 1.5 \times \text{UNL}$ $\leq 3 \times \text{UNL}$ if hepatic involvement with CLL
	Potassium and calcium	Within normal limits for laboratory (supplementation permitted)
	Glucose (fasting)	$< 7.8 \text{ mmol/L}$ (AND HbA1c $\leq 8\%$ if diabetic)

* Creatinine clearance as calculated by Cockcroft-Gault formula or by 24 hour urine measurement:

Females:
$$\text{GFR} = \frac{1.04 \times (\text{140-age}) \times \text{weight in kg}}{\text{serum creatinine in } \mu\text{mol/L}}$$

Males:
$$\text{GFR} = \frac{1.23 \times (\text{140-age}) \times \text{weight in kg}}{\text{serum creatinine in } \mu\text{mol/L}}$$

** Direct if patient known to have Gilbert's syndrome

AMEND #1: 2015-OCT-22; AMEND #3: 2016-AUG-24

5.1.8 Patient consent must be obtained according to local Institutional and/or University Human Experimentation Committee requirements. It will be the responsibility of the local participating investigators to obtain the necessary local clearance, and to indicate in writing to the CCTG Study Coordinator that such clearance has been obtained, before the trial can commence in that centre. Because of differing requirements, a standard consent form for the trial will not be provided but a sample form is provided on the IND.216 webpage. A copy of the initial REB approval and approved consent form must be sent to the central office. The patient must sign the consent form prior to registration and prior to tests which are considered to be study specific (see Section 6). Please note that the consent form for this study must contain a statement which gives permission for the CCTG and monitoring agencies to review patient records.

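### Protocol 8.4.3: for AST/ALT grade 3 recurring at grade 3 after a reduced-dose restart, one footnote says resume lower and another says stop, and the text does not rank them

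*Protocol*

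**What the plan says.** The AST/ALT part of the table in Protocol 8.4.3 has a row for a rise of two grades from baseline. It lists two triggers, grade 0 to grade 2 and "Grade 1 to Grade 3", and both carry the three-asterisk mark. The action is to hold drug until recovery to grade 1 or less, "then reduce 1 dose level", and that instruction carries the two-asterisk mark. Without recovery within 28 days, drug stops.

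The footnotes say, for a recurrence after restart:

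- Two asterisks, same grade: "if the same toxicity recurs with the same severity, then the next treatment should be resumed at a lower dose regardless of duration".
- Two asterisks, worse grade: "If the same toxicity occurs with a worse severity, then the patient must discontinue treatment with buparlisib".
- Three asterisks: a cross-reference to the combined AST/ALT and bilirubin stop, followed by "In case of recurring Grade 3 or higher toxicity after re-challenge, buparlisib should be permanently discontinued".
- Four asterisks: "If a third dose reduction is required or therapy is delayed by > 28 days, patients must discontinue protocol therapy".

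Grade 4 AST/ALT has its own row, which stops drug. Section 8.4 sets 20 mg per dose level and at most two reductions per patient. It also has a tie-break for conflicting recommendations (take the lowest dose), worded for a patient with more than one toxicity.

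**The concern.** A patient whose AST/ALT goes from grade 1 to grade 3, recovers, restarts one level lower and reaches grade 3 again meets the same-grade condition of the two-asterisk footnote and the grade 3 condition of the three-asterisk footnote. The first tells the site to go on at a lower dose; the second tells it to stop for good.

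The layout makes the wrong choice easy. The two-asterisk text is standard wording used in most of the other 8.4 toxicity tables, and its mark sits beside the dose instruction. The stop rule is the second sentence of a footnote that opens with a bilirubin criterion. A site that follows the two-asterisk text re-exposes a patient after a second grade 3 liver event, against a stop rule attached to the same row. A site that stops could be queried for departing from the two-asterisk text.

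**Working it through.** The plan gives no figure for this path, so there is none to reproduce. The check traces each recurrence through the footnotes, then works out the dose at stake and how often the path could arise.

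**1. Recurrence paths on the two-grade-increase row**, after a reduced-dose restart, with one reduction still available and bilirubin not above 2 x ULN:

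| First event, then recurrence | Two-asterisk footnote | Three-asterisk footnote | Grade 4 row | Result |
|---|---|---|---|---|
| Grade 2, then 2 | resume lower | not triggered | no | resume lower |
| Grade 2, then 3 | stop (worse grade) | not needed | no | stop |
| Grade 2, then 4 | stop (worse grade) | not needed | stop | stop |
| Grade 3, then 3 | resume lower | stop | no | **conflict** |
| Grade 3, then 4 | stop (worse grade) | stop | stop | stop |

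Only grade 3 followed by grade 3 is contradictory. If both reductions have been used, the four-asterisk footnote stops drug there too. The bilirubin rows do not carry the three-asterisk mark and are not affected.

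**2. Does any other text settle it?**

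- The four-asterisk footnote does not: the path needs neither a third reduction nor a hold beyond 28 days.
- The combined AST/ALT and bilirubin stop does not: it needs bilirubin above 2 x ULN.
- The 8.4 tie-break does not, read literally: this is one toxicity with two footnotes, not several toxicities.
- The strength of the wording does not: both instructions are phrased as what should be done.

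**3. Dose at stake** (starting doses from 8.1.1; 20 mg per level and two reductions at most from 8.4):

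- 100 mg start: 100 − 20 = 80 mg at the first restart. At recurrence, 80 − 20 = 60 mg under two asterisks, against 0 mg under three.
- 80 mg fallback start: 80 − 20 = 60 mg, then 60 − 20 = 40 mg against 0 mg.

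**4. Frequency.** As printed, the row reaches grade 3 only from a baseline of grade 1. Section 5.1.7 caps AST/ALT at entry at 1.5 x UNL, or 3 x UNL "if hepatic involvement with CLL". The patient then needs two grade 3 events, recovery from each within 28 days, and an unused reduction. Maximum accrual in 14.2 is 12 + 17 = 29.

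The documents give no rate for this path. *Assumption:* the per-patient probability p of the whole path lies between 0.1% and 2%. Expected patients = 29p; chance of at least one = 1 − (1 − p)^29.

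| p | Expected patients | Chance of at least one |
|---|---|---|
| 0.001 | 0.029 | 1 − 0.999^29 = 2.9% |
| 0.01 | 0.29 | 1 − 0.99^29 = 25.3% |
| 0.02 | 0.58 | 1 − 0.98^29 = 44.3% |

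The expected number reaches one patient only at p = 1/29 = 3.4%.

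**The case against.** The best reply is that ordinary reading resolves the conflict. The three-asterisk rule is specific to these AST/ALT triggers and to grade 3 or higher, whereas the two-asterisk text is general wording. If the general text prevailed, the specific stop rule would do almost nothing, because worse-grade and grade 4 recurrences stop anyway. The 8.4 tie-break, though worded for several toxicities, leans the same way.

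The harm is also limited. Restart requires recovery to grade 1 or less. Liver tests are at least weekly until then and every other week afterwards. Grade 4, or raised AST/ALT with bilirubin above 2 x ULN, stops drug. Reductions are capped at two, and the central office monitors adverse events throughout. Finally, the frequency range is assumed, and its upper end comes entirely from the chosen 2% ceiling.

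Most of this stands. The intended rule is clear enough to infer, the safeguards are real, and the frequency figures show scale only; the point does not depend on them. What the reply does not remove is that two operative safety instructions on one row say opposite things and the protocol never says which prevails. Section 8.4 names transaminitis first among the most frequent buparlisib toxicities, so liver events on this drug are to be expected.

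**Conclusion.** The inconsistency is real and minor. It is confined to grade 3 AST/ALT recurring at grade 3 after a reduced-dose restart, with bilirubin not above 2 x ULN, recovery within 28 days and one reduction unused. There the instructions differ by 60 mg daily against none, or 40 mg against none from the fallback start. The stop rule exists and evidently governs, which leaves the two-asterisk footnote to cover same-grade recurrence at grade 2; what is missing is an exception in that footnote. That the stop rule governs is an inference from its specificity and caution, not something the text states.

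Fewer than one patient would be expected to follow this path under the assumed range. The primary endpoint, the two-stage design and the planned analyses are untouched. Because a literal reading leads to re-exposure after a second grade 3 liver event, and the correction costs almost nothing, it should be fixed.

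**What to change.** At the next amendment, add to the two-asterisk footnote in 8.4.3: *except recurrent grade 3 or higher AST/ALT after re-challenge, for which buparlisib is permanently discontinued (see the three-asterisk footnote)*. Tell sites at the same time. The bilirubin rows can stay as printed.

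The cost is one clause and a site notice, with no added procedures, patients or analyses. The small downside is that a few patients lose a second reduced-dose restart, which the three-asterisk footnote already denies them.
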